9.1 MG-ADL score

The complete list of MG-ADL items and scores are provided in [Table 13-3](#). The total score will be calculated according to the rules set down in [Section 13.3](#).

The MG-ADL total score and change from Baseline will be summarized by study cycle, actual dose level received within study cycle, and RLZ total using descriptive statistics.

The above MG-ADL summaries will be repeated for COVID-19 free study participants, where COVID-19 free participants for this SAP exclude:

- Study participants who discontinue treatment due to suspected/confirmed COVID-19 infection (“Confirmed COVID-19” or “Suspected COVID-19” as the relationship to COVID-19 in the COVID-19 Impact eCRF);
- Study participants who discontinue treatment due to non-infection related COVID-19 issues (“General circumstances around COVID-19 without infection” or “other” as the relationship to COVID-19 in the COVID-19 Impact eCRF);
- Study participants have visits affected in treatment period (eg visit performed by video call) due to COVID-19 pandemic.

The subgroup summaries will be performed as specified in [Section 4.9.1](#). Additional summary by fixed dose and weight subgroups will also be conducted as specified in [Section 4.9.2](#).

The MG-ADL total score (excluding ocular items) with associated change from Baseline will be summarized by study cycle, actual dose level received within study cycle, and RLZ total using descriptive statistics.

The mean change from Baseline in MG-ADL over time will be plotted by study cycle and treatment group.

A boxplot of change from Baseline in MG-ADL at Day 43 will be generated by study cycle and administered dose as specified in [Section 4.9.2](#).

By-participant listings of MG-ADL values will be provided. In addition, listing of MG-ADL by study cycle and dose will also be provided.

9.2 QMG score

The complete list of QMG items and scores are provided in [Table 13-1](#). Partially missing total scores will be imputed according to the rules set down in [Section 13.1](#).

The QMG total score and QMG total score (excluding ocular items) with associated change from Baseline will be summarized by study cycle, actual dose level received within study, and RLZ total using descriptive statistics.

The subgroup summaries (by MuSK+ or AChR+ only) will be performed as specified in [Section 4.9.1](#). Additional summary by fixed dose and weight subgroups will also be conducted as specified in [Section 4.9.2](#).

The mean change from Baseline in QMG over time will be plotted by study cycle and treatment group.

A boxplot of change from Baseline in QMG at Day 43 will be generated by study cycle and administered dose as specified in [Section 4.9.2](#).

By-participant listings of QMG scores will be provided.

9.3 MG-C score

The complete list of MG-C items and scores are provided in [Table 13–2](#). The MG-C total score and MG-C total score (excluding ocular items) will be calculated according to the rules set down in [Section 13.2](#).

The MG-C total score and total score (excluding ocular items) with associated change from Baseline will be summarized by study cycle, actual dose level received within study, and RLZ total using descriptive statistics.

The subgroup summaries (by MuSK+ or AChR+ only) will be performed as specified in [Section 4.9.1](#). Additional summary by fixed dose and weight subgroups will also be conducted as specified in [Section 4.9.2](#).

The mean change from Baseline in MG-C over time will be plotted by study cycle and treatment group.

A boxplot of change from Baseline in MG-C at Day 43 will be generated by study cycle and administered dose as specified in [Section 4.9.2](#).

By-participant listings of MG-C scores will be provided.

9.4 MG Symptoms PRO

The MG Symptoms PRO scale scores will be calculated according to the rules set down in [Section 13.4](#).

The MG Symptoms PRO ‘Muscle Weakness Fatigability’, ‘Physical Fatigue’ and ‘Bulbar Symptoms’ scale scores and changes from Baseline will be summarized by study cycle, actual dose level received within study cycle, and RLZ total using descriptive statistics.

The subgroup summaries (by MuSK+ or AChR+ only) will also be performed as specified in [Section 4.9.1](#).

The mean change from Baseline in MG Symptoms PRO over time will be plotted by study cycle and treatment group.

By-participant listings of MG Symptoms PRO scale scores will be provided separately.

9.5 MG-ADL responder rate (≥ 2.0 points improvement from Baseline)

Study participants will be classified as MG-ADL total score responders at a scheduled visit if there is an improvement (decrease of at least a 2-points) from Baseline in the MG-ADL total score.

The number and percentage of observed MG-ADL responders at each scheduled post-Baseline visit will be summarized by study cycle, actual dose level received within study cycle, and RLZ total using descriptive statistics.

Additional summary of observed MG-ADL responders by fixed dose and weight subgroups will also be conducted as specified in [Section 4.9.2](#).

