9.2.1 Intercurrent event handling rationale and impact on the study

In MG0007, every study participant, except those coming from MG0004, will start with an initial fixed mandatory cycle. Prior to dosing in the initial fixed treatment cycle, the study participant will be assessed for MG worsening (eg, an increase of 2.0 points on the MG-ADL or 3.0 points on the QMG scale). The study participant will be initially randomized to rozanolixizumab equivalent to approximately 7mg/kg or 10mg/kg weekly (QW). After the first treatment cycle, dose adjustments may be applied at the start of each treatment cycle based on Investigator's discretion. Dose adjustments may not be applied during a treatment cycle.

For the assessment of safety and tolerability, adverse events (AEs) recorded up to 8 weeks after the last sc infusion will be utilized for main analyses, regardless of study participants receiving treatment with rescue therapy.

For the analyses of efficacy endpoints, the intercurrent events to be considered are the use of rescue therapy prior to Day 43 and permanent treatment discontinuation (or withdrawal from study) due to TEAEs. Efficacy endpoints will be summarized in line with a treatment policy approach. With this approach, rozanolixizumab results will be analyzed regardless of study participants receiving treatment with rescue therapy. Summaries will also be presented for the efficacy endpoints where participants will be censored at the time that they take rescue medication.

Missing values will not be imputed.

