3 DATA ANALYSIS CONSIDERATIONS

3.1 General presentation of summaries and analyses

For safety analyses, data will be summarized by dose levels of rozanolixizumab at the time of the event or measurement. For efficacy analyses, data will be summarized by the dose first received in the study. Additionally, efficacy data will be summarized by dose levels of rozanolixizumab received in each treatment cycle.

Statistical analysis and generation of tables, figures, participant data listings, and statistical outputs will be performed using SAS® Version 9.3 or higher. All tables and listings will use Courier New font size 9.

Descriptive statistics will be displayed to provide an overview of the study results. For continuous variables, descriptive statistics will include number of participants with available measurements (n), mean, standard deviation (SD), median, minimum, and maximum.

For categorical variables, the number and percentage of participants in each category will be presented. Unless otherwise noted, the denominator for percentages will be based on the number of participants included in the respective analysis set. Participants with missing data can generally be accounted for using the following approaches:

- For summaries of demographics and Baseline characteristics: summarize percentages based on all participants in the analysis set and include a “Missing” category (corresponding to participants with missing data for the variable being summarized) as the last row in the list of categories being summarized.
- For summaries of efficacy and safety endpoints, unless otherwise specified: summarize percentages based only on those participants with observed data for the variable being summarized. As the denominator may be different from the number of participants in the

analysis set being considered, the denominator should be displayed in the table. The general format for displaying this will be “n/Nsub (%).”

Unless otherwise noted, all percentages will be displayed to one decimal place. No percentage will be displayed for zero counts, and no decimal will be presented when the percentage is 100%.

For the purpose of the tabulations the lower and upper confidence limits for the percentages will be truncated at 0 and 100% respectively.

For PK concentration data, summary statistics will include geometric mean, geometric coefficient of variation (geoCV), 95% confidence interval (CI) for geometric mean, arithmetic mean, SD, median, minimum, and maximum.

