9.6 Time to first MG-ADL response

Time to First MG-ADL response (in days) by study cycle is defined as Date of First post-Baseline MG-ADL Response (≥ 2.0 points improvement from Baseline) within study cycle - Date of first IMP within study cycle + 1. Participants will be excluded from the survival analysis for a cycle if they did not have IMP in that cycle.

Study participants who use rescue therapy within study cycle before achieving first MG-ADL response within study cycle will be censored at time of rescue intake. For non-responders who take rescue therapy, they will be censored at the date taken rescue therapy, or last non-missing post Baseline MG-ADL visit, whichever is earlier. For non-responders who do not take rescue therapy, they will be censored at the last non-missing post-Baseline MG-ADL visit date.

The survival estimates of 1, 8, 15, 22, 29, 36, 43, 71, 99, 127, 155, 180, 300, 400, 500, 600, 700, 800, 900 and 1000 days to first MG-ADL response, median times to MG-ADL response with 95% CI, and cumulative number of events by study cycle will be calculated using Kaplan-Meier method for RLZ dose level received within study cycle and RLZ total. Number of censored study participants will be reported as well. A Kaplan-Meier plot will also be generated by study cycle and treatment group.

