9.7 QMG responder rate (≥ 3.0 points improvement from Baseline)

Participants will be classified as QMG total score responders at a scheduled visit if the QMG total score is at least a 3-point improvement (decrease) from Baseline.

The number and percentage of observed QMG responders at each scheduled post-Baseline visit will be summarized by study cycle, actual dose level received within study cycle, and RLZ total using descriptive statistics.

Additional summary of observed QMG responders by fixed dose and weight subgroups will also be conducted as specified in [Section 4.9.2](#).

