9.12 Minimal Symptom Expression

The Minimal Symptom Expression is defined as MG-ADL score of 0 or 1 (Vissing et al. 2020). The complete list of MG-ADL items and scores are provided in [Table 13-3](#). The total score will be calculated according to the rules set down in [Section 13.3](#).

The number and percentage of participants achieving Minimal Symptom Expression at any time during the Treatment and Observation Periods will be summarized by study cycle, actual dose level received within study cycle, and RLZ total using descriptive statistics.

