13.3 Myasthenia Gravis-Activities of Daily Living

The MG-ADL score comprises 8 items, each with a score of 0 to 3. The total score is obtained by summing the responses to each individual item. Thus, the score ranges from 0 to 24 with a higher score indicating more disability. The MG-ADL testing form is provided in [Table 13-3](#).

In the event of missing data, the following rules will be applied:

- If 1 or 2 items are not answered, the overall score will be obtained by imputing the missing items with the average score across the remaining items at the specific visit. The imputed value will be rounded to one decimal place
- If more than 2 items are missing the overall score will not be calculated.

Table 13-3: MG-Activities of Daily Living

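### Participants who start a cycle below the responder threshold cannot respond but stay in the denominator, which can distort comparisons of response between cycles

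*SAP*

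**What the plan says.** SAP 9.5 defines an MG-ADL responder at a scheduled visit as someone in whom "there is an improvement (decrease of at least a 2-points) from Baseline in the MG-ADL total score". SAP 9.7 sets the QMG rule as follows: the "QMG total score is at least a 3-point improvement (decrease) from Baseline". SAP 9.8 uses the same 3-point rule for MG-C. None of these sections sets a condition on the Baseline score.

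All three totals start at 0. For MG-ADL, SAP 13.3 states: "Thus, the score ranges from 0 to 24 with a higher score indicating more disability". QMG runs from 0 to 39 (SAP 13.1) and MG-C from 0 to 50 (SAP 13.2).

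For efficacy percentages, the SAP 3.1 rule is to "summarize percentages based only on those participants with observed data for the variable being summarized". For time to first MG-ADL response, the only exclusion in SAP 9.6 is: "Participants will be excluded from the survival analysis for a cycle if they did not have IMP in that cycle". Non-responders without rescue are censored at their last MG-ADL visit.

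Protocol 9.2.1 states that "every study participant, except those coming from MG0004, will start with an initial fixed mandatory cycle". Worsening is assessed before that first dose, but dosing does not depend on it, and Protocol 5.1 sets no minimum score. Participants from MG0004 start their first MG0007 cycle on worsening, and so do later cycles generally (Protocol 4.1).

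**The concern.** MG-ADL response and time to MG-ADL response are secondary endpoints for each of the first three cycles. The study rationale includes learning how response holds up in subsequent cycles, so readers will set the cycle tables side by side.

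For a participant below the threshold, the responder rule gives the same answer for every possible outcome. The SAP itself treats such scores as attainable: "The Minimal Symptom Expression is defined as MG-ADL score of 0 or 1" (SAP 9.12). Someone who starts a cycle at 1 and stays there has Minimal Symptom Expression in one table and is a treatment non-responder in another.

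If the share of such participants differs between cycles, the reported response rates will differ even when response among those able to respond is the same. No planned table would show this. The Baseline MG-ADL split in SAP 4.9.1 is cut at 5 and covers MG-ADL scores and change only. The responder rates in SAP 9.5, 9.7 and 9.8 get only dose and weight subgroups.

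**Working it through.** The plan gives no expected responder rate, median time to response or Baseline distribution, so there is no figure of its own to reproduce. The threshold step below is exact. The sizes rest on assumed values, shown as ranges.

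**1. Who cannot respond.** The largest possible fall equals the Baseline score. A fall of 2 is impossible if MG-ADL Baseline is below 2: scores 0 and 1, and any fractional score below 2 that arises from item imputation under SAP 13.3. A fall of 3 is impossible if QMG or MG-C Baseline is 0, 1 or 2.

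**2. Effect on the responder rate.** Let f be the share of a cycle below threshold and r the response rate among the rest. Then reported rate = (1 − f) × r + f × 0 = (1 − f) × r, and the shortfall is f × r.

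**3. Effect on time to response.** Participants below threshold are never events. With complete follow-up, cumulative response is (1 − f) × F(t), where F(t) is the curve among those able to respond. To illustrate, assume that 70% of those able to respond do so by Day 43, with a constant chance per visit over Days 8, 15, 22, 29, 36 and 43 and no first response after that. Then:
- F(29) = 1 − 0.30^(4/6) = 55.2%
- F(36) = 1 − 0.30^(5/6) = 63.3%
- F(43) = 70%

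At f = 10%, Day 29 gives 0.9 × 55.2% = 49.7%, just under half, so the median moves to Day 36 (0.9 × 63.3% = 57.0%). At f = 20%, Day 36 gives 0.8 × 63.3% = 50.7%. At f = 30% the curve stops at 0.7 × 70% = 49%.

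| f (assumed) | Reported rate if r = 70% | Shortfall, points | Median time to response |
|---|---|---|---|
| 0 | 70% | 0 | Day 29 |
| 5% | 66.5% | 3.5 | Day 29 |
| 10% | 63% | 7 | Day 36 |
| 20% | 56% | 14 | Day 36 |
| 30% | 49% | 21 | not reached |

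For f from 5% to 30% and r from 50% to 80%, the shortfall runs from 0.05 × 50 = 2.5 to 0.30 × 80 = 24 points.

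**4. How f could arise in cycle 1.** Cycle 1 mixes mandatory MG0003 starts with worsening-driven MG0004 starts. If a share m is mandatory, a fraction f0 of those is below threshold, and none of the others is, then f = m × f0. With m = 50% (assumed):
- f0 = 5% gives f = 2.5% and 0.975 × 70% = 68.25%, a shortfall of 1.75 points.
- f0 = 20% gives f = 10% and 63%.
- Reaching f = 20% to 30% would need f0 = 40% to 60%.

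**5. Later cycles.** A cycle triggered by a rise of 2 MG-ADL points implies a score of at least 2 at the trigger. But Protocol 4.1 gives that rise only as an example, offers a 3-point QMG rise as an alternative, and leaves the decision to the Investigator. SAP 3.3 also fills a missing cycle Baseline from an earlier cycle or study, which may predate the worsening. MG-ADL Baselines below 2 can therefore still occur.

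**The case against.** The strongest reply is that nothing formal is at risk. All analyses are descriptive, no testing is planned, and the main efficacy endpoint is mean MG-ADL change. The all-participant rate correctly answers its own question: what share of treated and observed participants improved by at least 2 points. That stands, and for that reason the rate should be kept.

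It is also fair that some of the information is already visible. Baseline scores are summarized (SAP 6.2), lead-in study and worsening are tabulated (SAP 6.1), and MG-ADL is listed by cycle and dose (SAP 9.1), so a determined reader could recover MG-ADL counts below threshold. None of this carries through to the responder or Kaplan-Meier tables.

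The reply is strongest on size. The documents give no Baseline distribution. The category cut at 5 is not evidence of scores below 2, since a Baseline of 2, 3 or 4 can respond. Nothing in the documents shows that QMG or MG-C scores of 0 to 2 occur at entry. The upper part of the range would need a large share of mandatory-cycle entrants to be nearly symptom-free.

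A reader might go on to infer that cycle 1 rates are understated as a fact, or that any rise in response from cycle 1 to later cycles is spurious. The documents do not support either, because both need a value of f that is not given.

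**Conclusion.** The point holds conditionally. Certain non-response below the threshold is exact, and so is the retention of these participants in the denominator and risk set. The size is f × r for the responder rate, with a lower Kaplan-Meier curve and a median that is later or not reached. It is zero if nobody starts below threshold. At f = 10% in cycle 1, f = 0 in cycle 2 and r = 70% in both, the tables would show 63% and 70% with no difference among those able to respond.

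The effect is likely to be larger in cycle 1, because that is where dosing occurs without a worsening condition or minimum score. Three further readings are tempting but unsupported:
- Time to response is not made to look shorter. Participants who never become events lengthen it.
- The effect is not confined to cycle 1. Part of cycle 1 is worsening-driven, and later cycles can include low Baselines.
- The all-participant rate is not wrong. It becomes hard to interpret only when it is compared across groups with different f.

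This is a worthwhile, inexpensive improvement to a descriptive plan, not a flaw in its main endpoint.

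**What to change.** Keep the all-participant summaries in SAP 9.5 to 9.8 and add:
- the number and percentage below threshold by cycle and dose (MG-ADL below 2; QMG and MG-C below 3);
- supplementary responder rates in 9.5, 9.7 and 9.8 among participants with cycle Baseline MG-ADL of at least 2, QMG of at least 3 and MG-C of at least 3 respectively;
- a supplementary Kaplan-Meier analysis in 9.6 among those with cycle Baseline MG-ADL of at least 2;
- a sentence requiring the supplementary version to be shown alongside whenever response is compared between cycles or doses.

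This needs one filter on existing programs. If the counts are negligible, they settle the question. The cost is extra tables and a smaller n, mostly in cycle 1 if that is where low Baselines fall. The restriction does not make cycles fully comparable: selection into later cycles and regression to the mean remain, and a table footnote should say so.

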9.6 Time to first MG-ADL response

Time to First MG-ADL response (in days) by study cycle is defined as Date of First post-Baseline MG-ADL Response (≥ 2.0 points improvement from Baseline) within study cycle - Date of first IMP within study cycle + 1. Participants will be excluded from the survival analysis for a cycle if they did not have IMP in that cycle.

Study participants who use rescue therapy within study cycle before achieving first MG-ADL response within study cycle will be censored at time of rescue intake. For non-responders who take rescue therapy, they will be censored at the date taken rescue therapy, or last non-missing post Baseline MG-ADL visit, whichever is earlier. For non-responders who do not take rescue therapy, they will be censored at the last non-missing post-Baseline MG-ADL visit date.

The survival estimates of 1, 8, 15, 22, 29, 36, 43, 71, 99, 127, 155, 180, 300, 400, 500, 600, 700, 800, 900 and 1000 days to first MG-ADL response, median times to MG-ADL response with 95% CI, and cumulative number of events by study cycle will be calculated using Kaplan-Meier method for RLZ dose level received within study cycle and RLZ total. Number of censored study participants will be reported as well. A Kaplan-Meier plot will also be generated by study cycle and treatment group.

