2.2.2 Efficacy endpoints

2.2.2.1 Secondary efficacy endpoints

For each of the first 3 x 6-week treatment cycle, change from Baseline (Day 1) to Day 43^a:

- In MG-Activities of Daily Living (MG-ADL) score within one treatment cycle
- In Quantitative MG (QMG) score within one treatment cycle
- In MG-Composite (MG-C) score within one treatment cycle
- In MG Symptoms patient-reported outcomes (PRO) 'Muscle Weakness Fatigability' score within one treatment cycle
- In MG Symptoms PRO 'Physical Fatigue' score within one treatment cycle
- In MG Symptoms PRO 'Bulbar symptoms' score within one treatment cycle
- In MG-ADL responder (≥ 2.0 -point improvement) within one treatment cycle
- Time to MG-ADL response (≥ 2.0 -point improvement from Baseline [Day 1]) within one treatment cycle

For consecutive treatment cycles:

- Time between consecutive treatment cycles

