3.2.2 Study periods

The study cycle consists of the following:

- Treatment Period: 6 weeks
- Observation Period: 16 weeks
- Non-treatment period

The following definitions for starting and entering the study periods for each cycle will be applied:

- **Treatment Period** starts with the first day of IMP in each cycle in MG0007 and ends after Day 43 or PEOT assessments. All participants in the Safety Set will be considered to have started the Treatment Period. A participant is considered to have completed the Treatment Period of each cycle if assessments from Treatment Period Day 43 are completed.
- **Observation Period** starts with one day after the end of the Treatment Period of each cycle and ends after the final assessments at Day 155 visit. Participants with assessment on any Observation Period day are considered to have started the Observation Period.
- **Non-treatment period** starts with one day after the end of the Observation Period of each cycle and ends before the start of next cycle or the EOS assessment.

A study participant is considered to have completed the study if he/she has completed all phases of the study including the Observation Period and the EOS visit assessments. The end of the study is defined as the date of the last visit of the last participant in the study.

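### Time to first MG-ADL response is followed to Day 1000, beyond both endpoint windows, and censoring at rescue and retreatment makes the late Kaplan-Meier response estimates too high

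*SAP*

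**What the plan says.** The secondary version of the endpoint stands in SAP 2.2.2.1 under the lead-in "For each of the first 3 x 6-week treatment cycle, change from Baseline (Day 1) to Day 43", and is limited to one treatment cycle. SAP 2.2.2.2 repeats it as an other efficacy endpoint covering the treatment cycle and the Observation Period. SAP 3.2.2 ends the Observation Period at the Day 155 visit.

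SAP 9.6 measures from the first infusion of a study cycle to the "Date of First post-Baseline MG-ADL Response" within that cycle. One visit with at least 2 points of improvement is enough; no confirmation is required. Under SAP 3.2.2 a study cycle also contains a non-treatment period, which "starts with one day after the end of the Observation Period of each cycle and ends before the start of next cycle" or at the end-of-study assessment, so it has no fixed length. Survival estimates are listed at 20 landmarks, and the last nine read "180, 300, 400, 500, 600, 700, 800, 900 and 1000 days to first MG-ADL response".

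On censoring, 9.6 says that participants who use rescue before a response "will be censored at time of rescue intake" (a rescued non-responder at the earlier of rescue and the last MG-ADL visit). It adds: "For non-responders who do not take rescue therapy, they will be censored at the last non-missing post-Baseline MG-ADL visit date". Starting a new cycle is not mentioned.

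**The concern.** Two separate things go wrong.

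**The event.** The last scheduled infusion is at Day 36. Protocol 6.5.1 lets corticosteroids and cholinesterase inhibitors change at any time, and asks for other gMG drugs to be held stable only through the first 8 weeks of observation. A first 2-point drop at Day 300 may be symptom fluctuation or the effect of a background drug, yet 9.6 credits it to the cycle. The landmarks from Day 180 on match neither endpoint definition, and SAP 3.9 does not list the longer horizon among the changes from the protocol.

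**The censoring.** Rescue is for symptoms that persist despite treatment, and a new cycle is started on worsening. Kaplan-Meier treats participants removed for either reason as if they would have gone on to respond at the rate of those still at risk. Read as a cumulative proportion of responders, one minus Kaplan-Meier is then too high. At late times it describes a shrinking group who had neither responded nor needed more treatment.

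**Working it through.** **No plan figure to reproduce.** The documents give no response, rescue, retreatment or late-improvement rate for this endpoint. Every rate below is an assumption.

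**Windows.** Day 43 = 1 + 6×7 and Day 155 = 43 + 16×7. Of the 20 landmarks, 7 lie at or before Day 43, 4 run from Day 71 to Day 155, and 9 lie after Day 155.

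**What can censor, and when.** SAP 2.3.1 sets the usual earliest next cycle at 4 weeks after the last dose: Day 36 + 28 = Day 64. Up to Day 43, therefore, only rescue normally acts. Retreatment becomes censoring because the event must fall within the study cycle, the cycle stops at the next one (3.2.2), and an unrescued non-responder is censored at the last MG-ADL visit (9.6).

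**Formulas.** At visit j let n be the number at risk and d the number of first responses.
- Kaplan-Meier: 1 − Π(1 − d/n).
- Cumulative incidence (Aalen-Johansen): Σ A·d/n, where A is the proportion with no response, rescue or new cycle before that visit.

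The two agree if nobody is rescued or retreated before responding. Otherwise A is smaller than the Kaplan-Meier survival, and every later response opens a gap.

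**Hand example.** Of 100 participants, 70 respond by Day 43 and 20 of the other 30 start a new cycle after Day 71. At Day 99, 2 of the 10 left improve and 4 more are then retreated. At Day 155, 1 of the 4 left improves.
- Actually responding: 73/100.
- 1 − KM = 1 − 0.30 × 0.80 × 0.75 = 0.82.

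**Worked rates.** Response and rescue by Day 43 are spread evenly over six weekly visits. From Day 71, each 4-weekly visit carries a 5% or 10% chance of a first 2-point drop, then a 25% chance of a new cycle. With 65% response, 5% rescue and 5% late improvement, the Kaplan-Meier survival is 0.330 at Day 43, and 0.330 × 0.95^4 = 0.269 at Day 155, so 1 − KM = 73.1%. For cumulative incidence, 30% remain after Day 43 and each visit keeps 0.95 × 0.75 = 0.7125 of them, so 0.65 + 0.30 × 0.05 × (1 + 0.7125 + 0.7125² + 0.7125³) = 68.9%. The Day 300 landmark uses the Day 295 visit.

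| Response / rescue by Day 43; late improvement per visit | Day 43: 1−KM vs incidence | Day 155 | Day 300 |
|---|---|---|---|
| 65% / 5%; 5% | 67.0 vs 65.0 | 73.1 vs 68.9 | 79.2 vs 70.0 |
| 65% / 5%; 10% | 67.0 vs 65.0 | 78.3 vs 72.3 | 87.2 vs 74.0 |
| 50% / 10%; 5% | 52.9 vs 50.0 | 61.6 vs 55.2 | 70.3 vs 56.6 |
| 50% / 10%; 10% | 52.9 vs 50.0 | 69.1 vs 59.8 | 81.8 vs 61.9 |

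**Wider range.** A simulation of 200,000 cycles per setting used response of 50% or 70%, rescue of 2% or 5% by Day 43 and 1% per visit later, and a new cycle at 15% or 35% per visit. With 5% or 10% late improvement per visit, the excess was 0.3-1.2 points at Day 43, 1.7-7.9 at Day 155, 5-20 at Day 300 and 12-35 at Day 1000. With no late improvement it stayed at or below about 1 point throughout.

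**Median.** In the 65%/5% settings both curves cross one half at the Day 36 visit (55.4 vs 54.2). In the 50%/10% settings both reach it at Day 43.

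**The case against.** The strongest reply is that rescue-censored Kaplan-Meier is no slip. Protocol 9.4.1 names Kaplan-Meier for this endpoint. Protocol 9.2.1 makes treatment policy the general approach and adds summaries censored at rescue. SAP 3.9 openly says that this endpoint uses the censored version. That stands, so cumulative incidence should be added and should not displace the named estimator. It does not answer the horizon, which 3.9 does not mention. Nor does it cover retreatment, or the lack of any companion estimate: SAP 4.7 plans no sensitivity analysis.

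There are also safeguards. SAP 9.6 reports numbers of events and of censored participants, SAP 9.5 tabulates observed responders by visit, and nothing is tested. These limit the harm, but by-visit percentages among those with data do not give a cumulative proportion responding.

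A reader might infer that the Day 43 result of the secondary endpoint is materially inflated by the long follow-up. It is not: a Kaplan-Meier estimate at Day 43 uses only data to Day 43, so capping follow-up there leaves every estimate up to that day unchanged. A reader might also infer that the median is seriously biased, but it does not move in the worked settings. Nor do the documents support calling every retreatment a treatment failure. Repeat cycles on worsening are the intended use (Protocol 2.1), at the investigator's discretion.

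**Conclusion.** The point holds for the late part of the curve. The landmarks from Day 180 to Day 1000 serve no defined endpoint, and the event rule lets unconfirmed late drops count as response. That one minus Kaplan-Meier exceeds the proportion actually responding, once rescue or retreatment precedes later counted responses, is a mathematical certainty.

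The size is not established, because it rests on assumed rescue, retreatment and late-improvement rates. Across the settings tried it is about 0.3-3 points at Day 43, about 2-9 at Day 155 and 5-20 near Day 300, and it nearly vanishes if late improvement does not occur. The median is little affected when at least half respond during treatment; if the on-treatment proportion sits just under one half, the two medians could separate. The consequence is a misleading descriptive curve, not a wrong inferential conclusion. Censoring at retreatment is a reading of 9.6 together with 3.2.2 and should be confirmed in the text.

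**What to change.** In SAP 9.6:
- End follow-up at Day 43 for the secondary endpoint, in each of cycles 1 to 3.
- For the other endpoint, end it at Day 155 or the first dose of the next cycle, whichever is earlier.
- Delete the Day 180-1000 estimates.
- State how a participant who starts a new cycle before responding is handled.
- Add the Aalen-Johansen cumulative incidence of response, with rescue and start of a new cycle before response as competing events, beside the rescue-censored Kaplan-Meier that the protocol names.

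The cost is a wording change and one extra output; no new data are needed. The reported cumulative response proportions will be slightly lower.
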